### 12.9.4 Physical Examination

Abnormal findings of physical examination will be presented in a by-subject listing.

### 12.9.5 Electrocardiogram (ECG)

Data will be listed, notable values will be flagged, and any other information collected will be listed as appropriate. Subjects with markedly abnormal ECG changes will be listed and tabulated separately. Observed changes will be analyzed descriptively by time of collection and treatment group.

### 12.10 Pharmacodynamic Analyses

Blood samples for pharmacodynamics (PD) assessments will be collected at Baseline and at Weeks 4, 8, 12, 16, 20, and 24. PD assessments will be conducted for all subjects, with the intent of evaluating psoriasis-associated inflammatory markers. PD analysis will be covered in a separate report

## 13.CHANGES FROM THE PROTOCOL AND PLANNED ANALYSES

Protocol states PP PGA will be analyzed using a similar method as NPSI, PSSI. The SAP summarizes PP PGA using frequency counts and percentages. Wilcoxon rank sum test will be used to compare the change from baseline in PP PGA between treatment groups.

## 14.FORMATting

Each page of the analysis will show the sponsor's name, the investigational product, and the protocol number. Report tables will be embedded in the MS Word report document from SAS program output without change. The footer of each table will show the name of the SAS program module which generated it, the names of all data sets providing input data in the program and the date and time the table was generated.

The SAS programs will generate rich-text-formatted (RTF) output with the "RTF" extension using the SAS Output Delivery System (ODS). The summary tables and listings will be formatted using the Times New Roman 9-point font. The RTF output is included in report documents prepared with Microsoft Word and converted to PDF format without typographical change.

Datasets will be created and taken as input to validated SAS programs to generate the report-ready tables, listings, and figures. Each output display will show the names of the data sets and SAS program used to produce it.

## **15.ARCHIVING AND RETENTION OF DOCUMENTS**

After finalization of the analysis, the following will be archived at Novella Clinical and/or with the study sponsor:

- SAP and any amendments
- All SAS code used in the project for statistical analysis, report tables generation, and analysis data set creation
- Tables, listings and figures as included in the clinical study report
- SAS study data tabulation model (SDTM) and analysis dataset model (ADaM) datasets

## 16. OUTLINE OF PROPOSED TABLES, FIGURES AND LISTINGS

Tables	
14.1	Summary of Disposition, Demographic, and Exposure Tables
14.1.1	Summary of Subject Disposition
14.1.2.1	Summary of Subject Demographics and Baseline Characteristics; Full Analysis Set
14.1.2.2	Summary of Subject Demographics and Baseline Characteristics; Safety Population
14.1.2.3	Summary of Subject Demographics and Baseline Characteristics; PP Population
14.1.3.1	Summary of Exposure and Compliance, Overall, Safety Population
14.1.3.2	Summary of Exposure and Compliance; Titration Period (Week 1—5), Safety Population
14.1.3.3	Summary of Exposure and Compliance; Treatment Period (Week 6 – 24), Safety Population
14.1.4.1	Summary of Prior Medications by Anatomical Therapeutic Chemical Class (ATC) and Preferred Term; Safety Population
14.1.4.2	Summary of Concomitant Medications by Anatomical Therapeutic Chemical Class (ATC) and Preferred Term; Safety Population
14.2.1	Summary of Primary Efficacy and Sensitivity Analysis Tables
14.2.1.1.1	Analysis of Co-Primary Efficacy Outcome PASI-75 Response Rate at Week 24, Full Analysis Set, Multiple Imputation
14.2.1.1.2	Analysis of Co-Primary Efficacy Outcome PASI-75 Response Rate at Week 24, PP Population, m-NRI
14.2.1.1.3	Analysis of Co-Primary Efficacy Outcome, Sensitivity Analysis, PASI-75 Response Rate at Week 24, Full Analysis Set, m-NRI
14.2.1.1.4	Analysis of Co-Primary Efficacy Outcome, Sensitivity Analysis, PASI-75 Response Rate at Week 24, Full Analysis Set, LOCF
14.2.1.1.5	Analysis of Co-Primary Efficacy Outcome, Sensitivity Analysis, PASI-75 Response Rate at Week 24, Full Analysis Set, OC
14.2.1.2.1	Analysis of Co-Primary Efficacy Outcome, IGA Treatment Success Rate at Week 24, Full Analysis Set, Multiple Imputation
14.2.1.2.2	Analysis of Co-Primary Efficacy Outcome, IGA Treatment Success Rate at Week 24, PP Population, m-NRI
14.2.1.2.3	Analysis of Co-Primary Efficacy Outcome, Sensitivity Analysis, IGA Treatment Success Rate at Week 24, Full Analysis Set, m-NRI
14.2.1.2.4	Analysis of Co-Primary Efficacy Outcome, Sensitivity Analysis, IGA Treatment Success Rate at Week 24, Full Analysis Set, LOCF
14.2.1.2.5	Analysis of Co-Primary Efficacy Outcome, Sensitivity Analysis, IGA Treatment Success Rate at Week 24, Full Analysis Set, OC
14.2.1.3.1	Analysis of Co-Primary Efficacy Outcome, Subgroup Analysis, PASI-75 Response Rate at Week 24 by Baseline hsCRP (mg/L), Full Analysis Set, Multiple Imputation
14.2.1.3.2	Analysis of Co-Primary Efficacy Outcome, Subgroup Analysis, PASI-75 Response Rate at Week 24 by Baseline BMI, Full Analysis Set, Multiple Imputation
14.2.1.3.3	Analysis of Co-Primary Efficacy Outcome, Subgroup Analysis, PASI-75 Response Rate at Week 24 by Occurrence of Diarrhea, Full Analysis Set, Multiple Imputation
14.2.1.4.1	Analysis of Co-Primary Efficacy Outcome, Subgroup Analysis, IGA Treatment Success Rate at Week 24 by Baseline hsCRP (mg/L), Full Analysis Set, Multiple Imputation
14.2.1.4.2	Analysis of Co-Primary Efficacy Outcome, Subgroup Analysis, IGA Treatment Success Rate at Week 24 by Baseline BMI, Full Analysis Set, Multiple Imputation
14.2.1.4.3	Analysis of Co-Primary Efficacy Outcome, Subgroup Analysis, IGA Treatment Success at Week 24 by Occurrence of Diarrhea, Full Analysis Set, Multiple Imputation
14.2.1.5.1	Analysis of Co-Primary Efficacy Outcome, PASI-75 Response Rate at Week 24 by Visit and Analysis Sites, Full Analysis Set, Multiple Imputation
14.2.1.5.2	Analysis of Co-Primary Efficacy Outcome, IGA Treatment Success at Week 24 by Visit and Analysis Sites, Full Analysis Set, Multiple Imputation
14.2.2	Summary of Secondary Efficacy Tables
14.2.2.1.1.1	Analysis of Secondary Efficacy Outcome - Change from Baseline in Total PASI Score by Visit, Double-Blind Treatment Period, Full Analysis Set, Multiple Imputation
14.2.2.1.1.2	Analysis of Secondary Efficacy Outcome - Percent Change from Baseline in Total PASI Score by Visit, Double-Blind Treatment Period, Full Analysis Set, Multiple Imputation

14.2.2.1.2.1	Analysis of Secondary Efficacy Outcome - Change from Baseline in Total PASI Score by Visit, Double-Blind Treatment Period, Full Analysis Set, LOCF
14.2.2.1.2.2	Analysis of Secondary Efficacy Outcome - Percent Change from Baseline in Total PASI Score by Visit, Double-Blind Treatment Period, Full Analysis Set, LOCF
14.2.2.1.3.1	Analysis of Secondary Efficacy Outcome - Change from Baseline in Total PASI Score by Visit, Double-Blind Treatment Period, Full Analysis Set, OC
14.2.2.1.3.2	Analysis of Secondary Efficacy Outcome - Percent Change from Baseline in Total PASI Score by Visit, Double-Blind Treatment Period, Full Analysis Set, OC
14.2.2.1.4.1	Analysis of Secondary Efficacy Outcome - Change from Baseline in Total PASI Score by Visit, Double-Blind Treatment Period, PP Population, OC
14.2.2.1.4.2	Analysis of Secondary Efficacy Outcome - Percent Change from Baseline in Total PASI Score by Visit, Double-Blind Treatment Period, PP Population, OC
14.2.2.2.1	Analysis of Secondary Efficacy Outcome: PASI-50 Response Rate by Visit, Double-Blind Treatment Period, Full Analysis Set, Multiple Imputation
14.2.2.2.2	Analysis of Secondary Efficacy Outcome: PASI-50 Response Rate by Visit, Double-Blind Treatment Period, Full Analysis Set, LOCF
14.2.2.2.3	Analysis of Secondary Efficacy Outcome: PASI-50 Response Rate by Visit, Double-Blind Treatment Period, Full Analysis Set, m-NRI
14.2.2.2.4	Analysis of Secondary Efficacy Outcome: PASI-50 Response Rate by Visit, Double-Blind Treatment Period, Full Analysis Set, OC
14.2.2.2.5	Analysis of Secondary Efficacy Outcome: PASI-50 Response Rate by Visit, Double-Blind Treatment Period, PP Population, m-NRI
14.2.2.3.1	Analysis of Secondary Efficacy Outcome: PASI-75 Response Rate by Visit, Double-Blind Treatment Period, Full Analysis Set, Multiple Imputation
14.2.2.3.2	Analysis of Secondary Efficacy Outcome: PASI-75 Response Rate by Visit, Double-Blind Treatment Period, Full Analysis Set, LOCF
14.2.2.3.3	Analysis of Secondary Efficacy Outcome: PASI-75 Response Rate by Visit, Double-Blind Treatment Period, Full Analysis Set, m-NRI
14.2.2.3.4	Analysis of Secondary Efficacy Outcome: PASI-75 Response Rate by Visit, Double-Blind Treatment Period, Full Analysis Set, OC
14.2.2.3.5	Analysis of Secondary Efficacy Outcome: PASI-75 Response Rate by Analysis Site and Visit, Double-Blind Treatment Period, PP Population, m-NRI
14.2.2.4.1	Analysis of Secondary Efficacy Outcome: IGA Success Rate by Visit, Double-Blind Treatment Period, Full Analysis Set, Multiple Imputation
14.2.2.4.2	Analysis of Secondary Efficacy Outcome: IGA Success Rate by Visit, Double-Blind Treatment Period, Full Analysis Set, LOCF
14.2.2.4.3	Analysis of Secondary Efficacy Outcome: IGA Success Rate by Visit, Double-Blind Treatment Period, Full Analysis Set, m-NRI
14.2.2.4.4	Analysis of Secondary Efficacy Outcome: IGA Success Rate by Visit, Double-Blind Treatment Period, Full Analysis Set, OC
14.2.2.4.5	Analysis of Secondary Efficacy Outcome: IGA Success Rate by Visit, Double-Blind Treatment Period, PP Population, m-NRI
14.2.2.5.1.1	Analysis of Secondary Efficacy Outcome: Change From Baseline in Percent of Affected Body Surface Area (BSA) by Visit, Double-Blind Treatment Period, Full Analysis Set, Multiple Imputation
14.2.2.5.1.2	Analysis of Secondary Efficacy Outcome: Percent Change from Baseline in Percent of Affected Body Surface Area (BSA) by Visit, Double-Blind Treatment Period, Full Analysis Set, Multiple Imputation
14.2.2.5.2.1	Analysis of Secondary Efficacy Outcome: Change From Baseline in Percent of Affected Body Surface Area (BSA) by Visit, Double-Blind Treatment Period, Full Analysis Set, LOCF
14.2.2.5.2.2	Analysis of Secondary Efficacy Outcome: Percent Change from Baseline in Percent of Affected Body Surface Area (BSA) by Visit, Double-Blind Treatment Period, Full Analysis Set, LOCF
14.2.2.5.3.1	Analysis of Secondary Efficacy Outcome: Change From Baseline in Percent of Affected Body Surface Area (BSA) by Visit, Double-Blind Treatment Period, Full Analysis Set, OC
14.2.2.5.3.2	Analysis of Secondary Efficacy Outcome: Percent Change from Baseline in Percent of Affected Body Surface Area (BSA) by Visit, Double-Blind Treatment Period, Full Analysis Set, OC
14.2.2.5.4.1	Analysis of Secondary Efficacy Outcome: Change From Baseline in Percent of Affected Body Surface Area (BSA) by Visit, Double-Blind Treatment Period, PP Population, OC
14.2.2.5.4.2	Analysis of Secondary Efficacy Outcome: Percent Change from Baseline in Percent of Affected Body Surface Area (BSA) by Visit, Double-Blind Treatment Period, PP Population, OC

14.2.2.6.1	Analysis of Secondary Efficacy Outcome: Change from Baseline in Nail Psoriasis Severity Index (NAPSI) of the target fingernail visit, Double-Blind Treatment Period, Full Analysis Set, Multiple Imputation
14.2.2.6.2	Analysis of Secondary Efficacy Outcome: Change from Baseline in Nail Psoriasis Severity Index (NAPSI) of the target fingernail visit, Double-Blind Treatment Period, Full Analysis Set, LOCF
14.2.2.6.3	Analysis of Secondary Efficacy Outcome: Change from Baseline in Nail Psoriasis Severity Index (NAPSI) of the target fingernail visit, Double-Blind Treatment Period, Full Analysis Set, OC
14.2.2.6.4	Analysis of Secondary Efficacy Outcome: Change from Baseline in Nail Psoriasis Severity Index (NAPSI) of the target fingernail visit, Double-Blind Treatment Period, PP Population, OC
14.2.2.7.1	Analysis of Secondary Efficacy Outcome: Change from Baseline in Psoriasis Scalp Severity Index (PSSI) by visit, Double-Blind Treatment Period, Full Analysis Set, Multiple Imputation
14.2.2.7.2	Analysis of Secondary Efficacy Outcome: Change from Baseline in Psoriasis Scalp Severity Index (PSSI) by visit, Double-Blind Treatment Period, Full Analysis Set, LOCF
14.2.2.7.3	Analysis of Secondary Efficacy Outcome: Change from Baseline in Psoriasis Scalp Severity Index (PSSI) by visit, Double-Blind Treatment Period, Full Analysis Set, OC
14.2.2.7.4	Analysis of Secondary Efficacy Outcome: Change from Baseline in Psoriasis Scalp Severity Index (PSSI) by visit, Double-Blind Treatment Period, PP Population, OC
14.2.2.8.1	Analysis of Secondary Efficacy Outcome: Change from Baseline in Palmoplantar Psoriasis Physician's Global Assessment (PP PGA) by Visit, Double-Blind Treatment Period, Full Analysis Set, Multiple Imputation
14.2.2.8.2	Analysis of Secondary Efficacy Outcome: Change from Baseline in Palmoplantar Psoriasis Physician's Global Assessment (PP PGA) by Visit, Double-Blind Treatment Period, Full Analysis Set, LOCF
14.2.2.8.3	Analysis of Secondary Efficacy Outcome: Change from Baseline in Palmoplantar Psoriasis Physician's Global Assessment (PP PGA) by Visit, Double-Blind Treatment Period, Full Analysis Set, OC
14.2.2.8.4	Analysis of Secondary Efficacy Outcome: Change from Baseline in Palmoplantar Psoriasis Physician's Global Assessment (PP PGA) by Visit, Double-Blind Treatment Period, PP Population, OC
14.2.2.9.1.1	Analysis of Secondary Efficacy Outcome: Change from Baseline in Pruritus Numeric Rating Scale (NRS) Score by Visit, Double-Blind Treatment Period, Full Analysis Set, Multiple Imputation
14.2.2.9.1.2	Analysis of Secondary Efficacy Outcome: Percent Change from Baseline in Pruritus Numeric Rating Scale (NRS) Score by Visit, Double-Blind Treatment Period, Full Analysis Set, Multiple Imputation
14.2.2.9.2.1	Analysis of Secondary Efficacy Outcome: Change from Baseline in Pruritus Numeric Rating Scale (NRS) Score by Visit, Double-Blind Treatment Period, Full Analysis Set, LOCF
14.2.2.9.2.2	Analysis of Secondary Efficacy Outcome: Percent Change from Baseline in Pruritus Numeric Rating Scale (NRS) Score by Visit, Double-Blind Treatment Period, Full Analysis Set, LOCF
14.2.2.9.3.1	Analysis of Secondary Efficacy Outcome: Change from Baseline in Pruritus Numeric Rating Scale (NRS) Score by Visit, Double-Blind Treatment Period, Full Analysis Set, OC
14.2.2.9.3.2	Analysis of Secondary Efficacy Outcome: Percent Change from Baseline in Pruritus Numeric Rating Scale (NRS) Score by Visit, Double-Blind Treatment Period, Full Analysis Set, OC
14.2.2.9.4.1	Analysis of Secondary Efficacy Outcome: Change from Baseline in Pruritus Numeric Rating Scale (NRS) Score by Visit, Double-Blind Treatment Period, PP Population, OC
14.2.2.9.4.2	Analysis of Secondary Efficacy Outcome: Percent Change from Baseline in Pruritus Numeric Rating Scale (NRS) Score by Visit, Double-Blind Treatment Period, PP Population, OC
14.2.2.10	Analysis of Secondary Efficacy Outcome, Time to Achieving PASI-75 Response, Full Analysis Set, OC
14.2.2.11	Analysis of Secondary Efficacy Outcome, Time to Achieving IGA Score of Clear or Almost Clear, Full Analysis Set, OC
14.2.3	Summary of Quality of Life (QoL) Tables
14.2.3.1	Analysis of Quality of Life Outcome: Change from Baseline in QIDS-SR16 Total Score by Visit, Full Analysis Set, OC
14.2.3.2.1	Analysis of Quality of Life Outcome: Change from Baseline in DLQI Total Score by Visit, Full Analysis Set, OC
14.2.3.2.2	Analysis of Quality of Life Outcome: Change from Baseline in DLQI Individual Domains by Visit, Full Analysis Set, OC
14.2.3.3.1	Analysis of Quality of Life Outcome: Change from Baseline in SF-12 Subdomains by Visit, Full Analysis Set, OC

14.2.3.3.2	Analysis of Quality of Life Outcome: Change from Baseline in SF-12 Summary Scores by Visit, Full Analysis Set, OC
14.2.3.4	Analysis of Quality of Life Outcome: Change from Baseline in WPAI: PSO Score by Visit, Full Analysis Set, OC
14.2.3.5	Analysis of Quality of Life Outcome: Summary of HEOR Score by Visit, Full Analysis Set, OC
14.3	Summary of Safety Tables
14.3.1.1.1	Overall Summary of Adverse Events by Treatment, Titration Period, Safety Population
14.3.1.1.2	Overall Summary of Adverse Events by Treatment, Treatment Period, Safety Population
14.3.1.1.3	Overall Summary of Adverse Events by Treatment, Overall, Safety Population
14.3.1.2	Summary of Treatment-emergent Adverse Events by System Organ Class and Preferred Term in Descending Frequency, Safety Population
14.3.1.3	Summary of Treatment-emergent Adverse Events by System Organ Class, Preferred Term, and Maximum Severity, Safety Population
14.3.1.4	Summary of Treatment-emergent Adverse Events by System Organ Class, Preferred Term, and Maximum Causality, Safety Population
14.3.2.1	Summary of Clinical Laboratory Results by Treatment and Visit, Chemistry, Safety Population
14.3.2.2	Summary of Clinical Laboratory Results by Treatment and Visit, Hematology, Safety Population
14.3.2.3.1	Summary of Lymphocyte Counts by Clinical Response of PASI-50 at Week 24, Safety Population
14.3.2.3.2	Summary of Lymphocyte Counts by Clinical Response of PASI-75 at Week 24, Safety Population
14.3.2.4.1	Clinical Laboratory Results, Shifts from Baseline by Visit, Chemistry, Safety Population
14.3.2.4.2	Clinical Laboratory Results, Shifts from Baseline by Visit, Hematology, Safety Population
14.3.3.1	Summary of Vital Signs by Treatment and Visit, Safety Population
14.3.3.2	Summary of Vital Signs, Shifts from Baseline by Visit, Safety Population
14.3.4	Summary of ECG Results by Treatment and Visit, Safety Population
Figures	
14.3.1.1	Plot of Mean Change from Baseline by Visit, Lymphocyte Counts vs PASI scores, Safety Population, PPC-06 400 mg QD
14.3.1.2	Plot of Mean Change from Baseline by Visit, Lymphocyte Counts vs PASI scores, Safety Population, PPC-06 400 mg BID
14.3.1.3	Plot of Mean Change from Baseline by Visit, Lymphocyte Counts vs PASI scores, Safety Population, PPC-06 600 mg BID
14.3.1.4	Plot of Mean Change from Baseline by Visit, Lymphocyte Counts vs PASI scores, Safety Population, Placebo
14.3.2.1	Plot of Mean Change from Baseline by Visit, hsCRP vs PASI scores, Safety Population, PPC-06 400 mg QD
14.3.2.2	Plot of Mean Change from Baseline by Visit, hsCRP vs PASI scores, Safety Population, PPC-06 400 mg BID
14.3.2.3	Plot of Mean Change from Baseline by Visit, hsCRP vs PASI scores, Safety Population, PPC-06 600 mg BID
14.3.2.4	Plot of Mean Change from Baseline by Visit, hsCRP vs PASI scores, Safety Population, Placebo
Listings	
16.1.7	Subject Enrollment and Randomization, All Randomized Subjects
16.2.1.1	Screen Failure, All Screen Failure Subjects
16.2.1.2	Subject Disposition, All Randomized Subjects
16.2.2	Protocol Deviations, All Randomized Subjects
16.2.3	Population Datasets, All Randomized Subjects
16.2.4.1	Demographics and Baseline Characteristics, All Randomized Subjects
16.2.4.2	Prior and Concomitant Medication, All Randomized Subjects
16.2.4.3	Psoriasis Treatment History, All Randomized Subjects
16.2.4.4	Concurrent Procedures, All Randomized Subjects
16.2.4.5	Medical History, All Randomized Subjects

16.2.4.6	Psoriasis Medical History, All Randomized Subjects
16.2.5.1	Study Drug Accountability – Blister Packs, All Randomized Subjects
16.2.5.2	Study Drug Accountability – Bottles, All Randomized Subjects
16.2.5.3	Study Drug Exposure and Compliance, All Randomized Subjects
16.2.6.1.1	Psoriasis Area and Severity Index (PASI) score, All Randomized Subjects
16.2.6.1.2	PASI Change from Baseline and Responders, All Randomized Subjects
16.2.6.2	Investigator's Global Assessment (IGA) of Disease Severity, All Randomized Subjects
16.2.6.3	Investigator's Assessment of the Body Surface Area (BSA) Involvement of Psoriasis, All Randomized Subjects
16.2.6.4.1	Nail Psoriasis Severity Index (NAPSI) at Baseline, All Randomized Subjects
16.2.6.4.2	Target Nail Psoriasis Severity Index (NAPSI) , All Randomized Subjects
16.2.6.5	Psoriasis Scalp Severity Index (PSSI), All Randomized Subjects
16.2.6.6	Palmoplantar Physician's Global Assessment of Disease Severity (PP PGA), All Randomized Subjects
16.2.6.7	Itch by NRS, All Randomized Subjects
16.2.6.8	Self-Report Quick Inventory of Depressive Symptomatology (QIDS-SR16) , All Randomized Subjects
16.2.6.9.1	Dermatology Life Quality Index (DLQI) Individual Questions, All Randomized Subjects
16.2.6.9.2	Dermatology Life Quality Index (DLQI) Domains and Total Score, All Randomized Subjects
16.2.6.10.1	SF-12 Subdomains, All Randomized Subjects
16.2.6.10.2	SF-12 Individual Questions, All Randomized Subjects
16.2.6.11	Work Productivity and Activity Impairment Questionnaire: Psoriasis (WPAI: PSO), All Randomized Subjects
16.2.6.12	Health Economics and Outcome Research (HEOR), All Randomized Subjects
16.2.7.1	Adverse Events, All Randomized Subjects
16.2.7.2	Serious Adverse Events, All Randomized Subjects
16.2.7.3	Adverse Events Leading to Study Drug Discontinuation, All Randomized Subjects
16.2.8.1	Urine Pregnancy Test, All Randomized Female Subjects with Childbearing Potential
16.2.8.2.1	Clinical Laboratory Test Results; Chemistry, All Randomized Subjects
16.2.8.2.2	Clinical Laboratory Test Results; Hematology, All Randomized Subjects
16.2.8.2.3	Clinical Laboratory Test Results; Urinalysis, All Randomized Subjects
16.2.8.2.4	Clinical Laboratory Test Results; Lymphocyte, All Randomized Subjects
16.2.8.3	Laboratory Values Outside of Normal Range, All Randomized Subjects
16.2.8.4	Vital Signs, All Randomized Subjects
16.2.8.5	Abnormal Physical Examination Results
16.2.8.6.1	12-Lead ECG Results, All Randomized Subjects
16.2.8.6.2	12-Lead ECG Findings, All Randomized Subjects
16.2.8.7	Stool Consistency, All Randomized Subjects

Table 14.1.1: Summary of Subject Disposition

	PPC-06 400 mg QD	PPC-06 400 mg BID	PPC-06 600 mg BID	Placebo	Overall
Number of Subjects Screened					XX

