5.4 Discontinuation of Treatment or Assessments

Subjects can be removed from the study for any of the following reasons:

- AE(s)
- Protocol violation
- Withdrawal by subject (subject voluntarily discontinued study participation)
- Lost to follow-up
- Pregnancy
- Study terminated by sponsor
- Investigator decision
- Non-compliance with study drug (<80% or >120%)
- Loss of ability to freely provide consent through imprisonment or involuntary incarceration for treatment of either a psychiatric or physical (eg, infectious disease) illness
- Unblinding of a subject for any reason

All subjects meeting the above withdrawal criteria are to be evaluated at the safety follow-up EOS visits unless they have withdrawn full consent. The reason for a subject's permanent withdrawal is to be recorded on the appropriate electronic case report form (eCRF). Subjects

who prematurely withdraw from the study for AEs are to be monitored for up to 30 days after the subject stopped study treatment or until the abnormal parameter resolves or stabilizes.

Pregnancies are to be reported to the sponsor or designee within 24 hours of learning of its occurrence, and the pregnancy is to be monitored to determine outcome. Investigators are to document their attempts to contact subjects who are lost to follow-up.

As a class, FAEs are known to have an effect on lymphocyte and eosinophil counts and can have hepatotoxic and nephrotoxic effects at excessive exposures. The following study drug discontinuation criteria are to be implemented to reduce the risk of toxicity for individual subjects and to investigate the time course of recovery of affected safety parameters.

If any of the following criteria are met, study treatment will be permanently discontinued and the subject will be scheduled for an ETV followed by the Safety Follow-up Visit.

- Lymphocytes $<500/\text{mm}^3$ at any visit
- Lymphocytes $<800/\text{mm}^3$ on 3 consecutive visits
- ALT or AST $>8\times\text{ULN}$ on repeat examination (if assumed increase is related to study drug)
- ALT or AST $>5\times\text{ULN}$ for more than 2 weeks on repeat examination (if assumed increase is related to study drug)
- ALT or AST $>3\times\text{ULN}$ and either total bilirubin $>2 \times$ the ULN or International Normalized Ratio (INR) >1.5 on repeat examination (if assumed increase is related to study drug) in presence of normal alk phosphate.

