- ALT or AST $>3\times\text{ULN}$ with concurrent appearance or worsening of fatigue, nausea, vomiting, right upper quadrant pain or tenderness, fever, rash, or eosinophilia ($>5\%$ eosinophils on differential leukocyte count)
- Serum creatinine $>1.5\times\text{ULN}$ on repeat exam (if assumed increase is related to study drug)
- Proteinuria measured as 3+ or above in urine dipstick on 2 consecutive samples, 4 weeks apart
- If advised by the Medical Monitor or PML experts.

Laboratory tests can be repeated earlier than the next scheduled consecutive visit at the investigator's discretion and any associated safety issue should be followed up as per the Investigator's clinical judgment until resolution/stabilization.

Replacement Policy

Subjects who prematurely discontinue from the study after randomization will not be replaced.

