7.5.3 Safety Laboratory Assessments

Blood and urine samples for laboratory tests (hematology, serum biochemistry, and urinalysis) will be collected as specified in [Table 1-1](#). Clinical laboratory specimens will be analyzed by a central licensed and accredited laboratory facility according to the laboratory's standard operating procedures.

If any of the laboratory parameters of interest show a significant shift from baseline, subjects will then be scheduled for an interim visit within 2 weeks to repeat the laboratory measurements.

Non-fasting blood samples will be obtained at each visit for laboratory analysis of serum glucose, lipid panel, hsCRP, and PD study.

No blood is to be collected for the PD study at Screening.

Blood samples for serology assessment (HIV, HBsAg, Anti-HBc, and HCV) will be obtained at Visit 1 (Screening).

Lymphocyte subsets and antibody titer will be collected for safety assessments per [Table 1-1](#).

The routine clinical laboratory tests to be performed are provided in [Table 7-2](#).

The investigator may collect additional blood or urine samples to repeat any laboratory test that was abnormal post-dosing, or was within normal limits at Baseline, and is considered clinically significant. Abnormal laboratory results at the last scheduled visit may require additional collection of samples on an "as needed" basis until: a) the values return to the baseline value, b) the values are within normal limits, c) the values are clinically stable, or d) the investigator determines that further follow-up is unnecessary. The investigator will record the date and time of all additional samples collected. If the investigator establishes a clear explanation for the laboratory abnormality, he/she will record this explanation in the eCRFs.

Blood will also be collected and evaluated for PD study per [Table 1-1](#).

Table 7-2 Routine Clinical Laboratory Assessments

Hematology		
• Platelet Count	RBC Indices:	Automated WBC Differential:
• RBC Count	• MCV	• Neutrophils
• WBC Count (absolute)	• MCHC	• Lymphocytes
• Lymphocytes (absolute)	• MCH	• Monocytes
• Neutrophils (absolute)		• Eosinophils
• Monocytes (absolute)		• Basophils
• Hemoglobin		
• Hematocrit		
• Lymphocyte subset (collected and will be assessed)		
• Antibody titer (collected and stored with assessment done as required)		
Chemistry		
• Sodium	• Creatine Kinase	• Cholesterol
• Potassium	• Alkaline Phosphatase	• Triglycerides
• Chloride	• GGT	• HDL Cholesterol

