• Bicarbonate	• LDH	• LDL Cholesterol
• BUN	• Total Bilirubin	• Calcium
• Creatinine	• Direct Bilirubin	• Phosphorus
• AST (SGOT)	• Total Protein	• Uric Acid
• ALT (SGPT)	• Glucose (non-fasting)	• Magnesium
	• Albumin	• Creatinine Clearance
Routine Urinalysis		
• Appearance, color		
• pH, specific gravity		
• Glucose, blood, bilirubin, leukocyte esterase, ketones, nitrates		
• Urine protein, urine creatinine, protein:creatinine ratio		
• Microscopic examination (if indicated per clinical laboratory standards)		
Serology (Visit 1/Screening only)		
• HIV		
• HBsAg and Anti-HBc		
• HCV		

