## **12.9.2 Clinical Laboratory Testing**

Clinical laboratory values will be reported as complete listings of individual subject data. All laboratory values will be classified as normal, low, or high based on normal ranges supplied by the laboratory. Subjects with values outside the normal range will be flagged and summarized using shift tables. A separate listing and table will identify and summarize subjects with markedly abnormal values. For quantitative measures, observed and changes in clinical laboratory values will be analyzed descriptively by time of collection and treatment group.

Additionally, lymphocyte counts will be summarized by clinical response of PASI-50 and PASI-75 (Yes/No) at Week 24. Lymphocyte counts and hs-CRP will also be plotted against PASI scores by visit and treatment. The correlation coefficient will be reported.

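### SAP Section 16 gives urinalysis, including urine protein, by-subject listings only and omits the markedly abnormal laboratory table, contrary to SAP 12.9.2

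*SAP*

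**What the plan says.** Protocol 5.4 warns that fumaric acid esters "can have hepatotoxic and nephrotoxic effects at excessive exposures" and lists, among the criteria for permanent discontinuation of study drug, "Proteinuria measured as 3+ or above in urine dipstick on 2 consecutive samples, 4 weeks apart". Serum creatinine is a separate criterion in the same list. Protocol Table 7-2 puts "Urine protein, urine creatinine, protein:creatinine ratio" in the routine urinalysis panel. Table 1-1 schedules laboratory assessments, which include urinalysis, at Screening, Baseline, Weeks 4 to 24 and the early termination visit, and allows them at unscheduled visits.

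SAP 12.9.2 classes all laboratory values as low, normal or high and continues: "Subjects with values outside the normal range will be flagged and summarized using shift tables". It also commits to a listing and a table of markedly abnormal values, and to descriptive summaries of quantitative measures by visit and arm. Protocol 8.8.2 makes the same commitments. Neither text excepts urinalysis.

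In SAP Section 16 the by-visit laboratory summaries are one table for chemistry and one titled "Summary of Clinical Laboratory Results by Treatment and Visit, Hematology, Safety Population". The two shift tables cover the same two panels. Urinalysis has its own listing, "Clinical Laboratory Test Results; Urinalysis, All Randomized Subjects", and shares the listing of out-of-range values (16.2.8.3).

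**The concern.** The list and shells in Section 16 are what programmers build from. If they are followed, the analysis promised for every laboratory panel is not produced for the one panel that holds urine protein, and the markedly abnormal table is not produced for any panel. Safety and tolerability is a secondary objective of the trial, and proteinuria is one of its own stopping events. A reader of the study report would then have to count listing rows to learn whether graded proteinuria differs between the three doses and placebo.

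The conflict lies within the SAP, so the rule in Protocol 8.10 that the SAP prevails over the protocol does not settle it.

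**Working it through.** The plan states no figure on this point, so the check sets the commitment beside the planned outputs.

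| Panel | By-visit summary by arm | Shift table | Markedly abnormal table | Own listing |
|---|---|---|---|---|
| Promised in SAP 12.9.2 | yes | yes | yes | yes |
| Chemistry | 14.3.2.1 | 14.3.2.4.1 | none | 16.2.8.2.1 |
| Hematology | 14.3.2.2 | 14.3.2.4.2 | none | 16.2.8.2.2 |
| Urinalysis | none | none | none | 16.2.8.2.3 |

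1. *Is it only a slip in the table titles?* No. The chemistry summary shell is to be repeated for hematology and nothing else, and so is the chemistry shift shell. The listing shell names urinalysis explicitly. The panel was considered and was given listings only.

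2. *Is it a declared change?* No. SAP Section 13 records one departure from the protocol, the analysis of PP PGA.

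3. *Does another laboratory output cover proteinuria?* Chemistry includes creatinine, BUN and creatinine clearance. These measure renal function. Protocol 5.4 treats creatinine and proteinuria as separate criteria, so one does not stand in for the other. The disposition shell (Table 14.1.1) has no row for meeting a laboratory stopping criterion.

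4. *Would repeating the existing shells for urinalysis be enough?* Not fully, for three reasons.
   - Low, normal and high do not separate dipstick grades: if grades are recorded, every abnormal grade falls in one class.
   - The shells have rows for scheduled visits to Week 24. Under SAP 11.4 only the sample closest to the target day is used in each window, and an early termination sample more than 15 days after the last dose becomes Visit 9, which has no row. An extreme value can drop out.
   - The 5.4 criterion needs two consecutive samples 4 weeks apart, which cannot be read from visit-by-visit counts.

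5. *How much data is affected?* There are 6 scheduled on-treatment samples (Weeks 4, 8, 12, 16, 20, 24) and about 400 subjects, so at most 6 x 400 = 2,400 results. With the planned 50% dropout there are about 4 x 50 = 200 completers, who alone contribute 6 x 200 = 1,200 if they miss none. The number therefore lies roughly between 1,200 and 2,400.

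6. *Lymphocyte subsets.* Protocol 7.5.3 says "Lymphocyte subsets and antibody titer will be collected for safety assessments", and Table 1-1 schedules the draw at Baseline, Week 24 and early termination. The SAP does not name subsets. Table 7-2 files them under Hematology, so Tables 14.3.2.2 and 14.3.2.4.2 may include them. The separate lymphocyte listing drops its parameter column, which suggests a single parameter, but that says nothing about the content of the hematology tables.

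**The case against.** The strongest reply is that SAP 12.9.2 already requires the analysis. Urinalysis is not excepted there, Section 16 calls its contents proposed, and a careful programmer would add the missing tables. On that view this is an incomplete outline and not a decision to leave proteinuria unanalysed. That is a fair description of its nature. It does not remove the point, because the list and the shells agree with each other and disagree with the text, and nothing tells the programmer which governs.

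The second reply is that the risks are covered elsewhere. A reader might infer from the gap that neither kidney toxicity nor PML risk would be compared between arms. The documents do not support that. Creatinine, BUN and creatinine clearance have by-arm summary and shift tables. So does the absolute lymphocyte count, which is the measure used in the lymphocyte stopping criteria, and it is tabulated again by PASI response. Clinically relevant laboratory abnormalities are collected as adverse events, TEAEs are tabulated by arm, and events leading to discontinuation of study drug are counted by arm. Proteinuria reported as an adverse event would therefore reach a by-arm table. What remains is that this route depends on an investigator reporting it. The protocol reserves CTCAE grading for diarrhea and lymphocytopenia, so even a reported event would carry no proteinuria grade.

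A reader might also infer that lymphocyte subsets have no summary table. That is not established either, because Table 7-2 places them in Hematology. The supportable statement is that the SAP does not say where they are summarised.

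Finally, Table 7-2 does not state that dipstick grades are recorded. A display by grade must be conditional on that.

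**Conclusion.** The point holds for urinalysis and for the markedly abnormal table. Section 16 contradicts 12.9.2 and leaves proteinuria, a stopping criterion in Protocol 5.4, without a planned by-arm laboratory summary. Of the three kinds of summary promised, urinalysis has none; chemistry and hematology each have two and lack the third. The lymphocyte subset question is a minor clarification.

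The effect is confined to descriptive safety reporting. No efficacy analysis, error rate or clinical rule is touched. The documents give no expected rate of proteinuria, so no size of missed difference can be stated. The conclusion assumes that the programmed outputs follow Section 16. The count of subjects meeting the 5.4 criterion further assumes that the dipstick results used to apply it are in the database.

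**What to change.** Amend SAP Section 16 and its shells, with a matching sentence in 12.9.2:

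1. Add a by-arm urinalysis summary and shift table. Show urine protein by reported grade where grades are recorded, not only as low, normal or high. Include the worst post-baseline value, drawing on early termination and unscheduled samples, and the protein:creatinine ratio by visit.
2. Add the markedly abnormal laboratory table that 12.9.2 promises, with the number of subjects per arm who met the existing proteinuria criterion in Protocol 5.4. The SAP defines marked abnormality for vital signs but not for laboratory values, so the definition must be written in before the table can be programmed.
3. State whether lymphocyte subsets are in the hematology tables and, if so, show Baseline and Week 24 or last on-treatment (early termination) values. If not, name the table that holds them.

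The cost is about three descriptive tables from data the protocol already collects, two of them adapted from existing shells. No new assessment is needed.
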